The monitoring and analysis are fundamental elements of health policies and programs provide a set of essential tools that allow them to verify and improve their quality, efficiency, and effectiveness (Shamah-Levy *et al.*, 2018). The analysis of programs should start from the clear identification of the problems that need to be addressed and the understanding of the factors that associated to its origin that are susceptible to intervention. In this continuum, each phase in the life of a program is subject to an evaluation. The analysis of the different stages of a program facilitates the understanding whether the process is actually working to reach success. Each phase of the analysis of a program is in turn conceived as a product and an input, that is, the evidence is generated on a relevant and pertinent aspect of a program and feeds the development of an additional stage of evaluation (Shamah-Levy *et al.*, 2018).

The comprehensive analysis of public policies seeks to contribute to decision-making and social equity, generating knowledge and evidence on the effectiveness of programs for the best allocation of resources (Gutiérrez, 2017). It must be done at the beginning, during and after the program runs, starting from the idea of the program cycle through a staggered, interactive and interdependent sequence (Shamah-Levy *et al.*, 2018).⁵⁶ The implication of not having a comprehensive program analysis approach could lead to overestimating or underestimating the findings derived from the practice of a specific evaluation. An evaluation that does

not identify challenges, areas of opportunity or recommend improvements is a weak evaluation and its improving program performance is limited.

Research questions

- 1.- Does the current design of the School Health program contribute to improving the school environment through strategies aimed at promoting correct nutrition, adequate hydration, and increased MVPA?
- 2.- What are the barriers and facilitators for the implementation of the School Health program?
- 3.- What are the changes in the knowledge, attitudes, and practices that boys and girls from 3rd to 6th grade of primary have associated with the implementation of the School Health Program?
- 4.- What is the impact of the School Health program on physical activity levels, water, and fruit and vegetable consumption in girls and boys from 3rd to 6th grade of primary school?

5. Study Rationale

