- To analyze the impact of the School Health Program on schoolchildren physical activity levels, water consumption, and fruit and vegetable consumption.

7. Materials and methods

A comprehensive analysis of the design, implementation, results, and impact of the School Health Program will be carried out, which will be implemented in 58 schools in Mexico City during the first phase of implementation from October 2020. This study includes a design analysis of the Health School program, a quasi-experimental study to evaluate the impact of School Health on the individual outcomes of interest in the program (correct hydration, healthy eating, and physical activity), as well as an evaluation of the implementation. This analysis will be developed through three methodological stages which are presented in Figure 6. In this protocol is presented the first stage of implementation of this analysis only.

[figure not shown]

Figure 6. Stages, measurements and instruments of the Comprehensive analysis of Salud Escolar program

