7.2 Short-term results analysis (baseline measurement)

The results of Salud Escolar will be estimated by measuring changes in knowledge, attitudes, and practices related to correct nutrition, adequate hydration and physical activity. The Health and Nutrition Questionnaire, prepared by the Ministry of Health, will be used. This questionnaire has two versions [for 3rd grade of primary school (Appendix 3); and for 4th to 6th grade (Appendix 4) and consists of 3 main sections (Figure 6).The questionnaires were previously used in the Health in your School program. Data collection will be conducted by the Ministry of Health and the INSP research team will be solely responsible for data analysis.

Sample

The questionnaire is addressed to all girls and boys from 3rd to 6th grade (n = approximately 20,000 girls/boys) of the 58 primary schools selected for the implementation of the first phase of Salud Escolar. As part of Salud Escolar, staff from the Ministry of Health will go to the schools on the first day and give teachers a diptych announcing the Program, actions, and objectives (Appendix 5) and informed consent for parents. Teachers will send these documents in children's backpack and parents will review and return the signed consent (if given) on the next day.

Data collection

The Ministry of Health staff will apply the questionnaires with the support of the teaching staff. The questionnaires will be administered indoors (e.g. classroom) during school hours. Children whose parents have given their consent to participate will be included and children's oral assent will be obtained.

Data processing and analysis

Data will be coded by the Ministry of Health staff using an automated system and the database will be given to the INSP research team for subsequent analysis. A descriptive analysis of the data will be carried out, estimating means standard deviations for the continuous variables and proportions (%) for the categorical variables. Likewise, all available information will be disaggregated by sex and age.

[figure not shown]

Figure 7 Sections included in the Health and Food Questionnaire

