Table 6 presents the sample size necessary for hypotheses testing, considering a significance level of $\alpha = 0.05$, a statistical power of 80%, and a correlation of 0.2 between the basal and final measurements. Considering that the largest sample size required is the one to estimate the effect of the intervention on fruit and vegetable consumption ($n = 388$), a design effect of 2, and 20% losses to follow-up, it is estimated that a total of 980 girls and boys ($n = 490$ per intervention group) are needed.

A baseline measurement of 1000 girls and boys has been proposed. Considering the same assumptions of design effect and loss to follow-up, it was estimated that a sample size of 595 girls and boys is required for accelerometry measurements and the System for Observing Fitness Instruction Time (SOFIT).

Table 6 The sample size required to estimate expected differences

Indicator	Standard deviation	Expected difference	Sample size
Water consumption (ml/day)	631	171	384
MVPA (min/day)	40	10	248
MVPA (min/PE)	9	3.8	248
MVPA (min/recess)	12	3.9	244
Fruit and vegetable consumption (% of schoolchildren)		6.2%	388

Note. MVPA= moderate to vigorous physical activity; PE= physical education.

Schools selection

The intervention group schools will be selected randomly from the predefined list of 58 schools selected by the Ministries of Health and Education to participate in the first phase of implementation of Salud Escolar. The control group will be selected from a list of schools available in Mexico City provided by the Ministry of Education, where the program will not be implemented. Given that the selection of the 58 schools of the intervention group will not be at random, schools from the control group will be as similar as possible to those in the intervention group. Thus, it will be sought that the schools of both groups (i.e, intervention and comparison) are paired based on the following characteristics:

- Location: schools should be in the same geographical area < 5 km.
- Basic Geostatistical Area (BGA): within a similar BGA level
- Type of working day: in the same type of working day (regular, extended or full time)
- Hours: both in the morning or in the afternoon
- Size: schools from both groups will be expected to have a similar number of students and classes.

Participants

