For the evaluation of the individual indicators, boys and girls from 1st to 6th grade of primary school will be selected at random from the attendance lists of the school groups. A written consent from parents will be requested (Appendix 6) and an assent from the participants (Appendix 7). In the case of the evaluation of environmental indicators in schools, all schools' principals will be invited to participate and a written consent will be requested (Appendix 8).

Inclusion and exclusion criteria for schools and participants

Students who have provided assent to participate and who have the informed written consent of parents or caregivers will be eligible. Children who have a physical or mental disability to participate the program will be excluded.

Measurements

Healthy diet. Two instruments will be used, a 24-hour recall to estimate the total diet of schoolchildren, and food weighing to estimate food consumption within the school environment.

24-hour recall. This instrument will be used to measure and evaluate the total diet of schoolchildren. A 24-hour recall will be applied to mothers, fathers, or caregivers of participants responsible for feeding and preparing meals at home (Appendix 9). The registration system used for the National Health and Nutrition Surveys will be used (Shamah-Levy *et al.*, 2018). The 24-hour recall consists of an interview in which participants are asked to remember and describe all the food and beverages consumed the day before the interview, from the first intake of any food or drink, up to the last food or drink consumed before sleeping (Shim, Oh and Kim, 2014). The adult responsible for feeding the child will be asked to name, describe and quantify the amounts of all the food and drinks consumed by the participant the previous day. The information collected will include the characteristics of the food or drink, including preparation method, brands and quantity consumed (considering edible portion and total proportion consumed). Food and beverages consumed at school or outside the home without the adult being interviewed will be reported by schoolchildren. The instrument will be applied by trained staff and will be collected with the use of a laptop, using a software to collect 24-hour recalls in the Mexican population.

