Since part of the objectives of Salud Escolar is to improve the quality of the schoolchildren's diet and reduce the consumption of highly processed foods, the information obtained from the 24-hour recall will be used to evaluate the consumption of fruits and vegetables, sugar sweetened beverages (SSBs), and highly processed foods. A comparison will be conducted between participants consumption against the recommendations established in the Dietary and Physical Activity Guidelines in the Context of Overweight and Obesity in the Mexican Population (Bonvecchio, 2015). The proportion of schoolchildren who consume fruits and vegetables, and ultra-processed foods as outcome variables will be estimated.

Food and drink consumption during recess. Trained staff will record the food and drinks consumed during recess (snack or lunch) to objectively measure food consumption at school. Schoolchildren will be asked to show their lunch and beverages (brought from home or purchased at school) and what is contained will be recorded and weighted. This process will allow the detailed recording of the consumption of food and beverages at school campus, and the evaluation of the changes in food and beverages brought from home and purchased at school.

Correct hydration.

To analyze the impact of Salud Escolar on water consumption, a Beverage Diary will be applied to participants from 3rd to 6th grade (Appendix 10). The diary has been previously used and validated in different studies carried out by the INSP among schoolchildren (unpublished data) (Safdie *et al.*, no date; Pérez, 2016). Participants will receive a hard copy of the diary and will be asked to complete it at

home during three days. Data will be coded in Excel format and the consumption of water and SSBs (ml/day) will be estimated based on previously standardized procedures (Salud, 2015).

Physical activity

Direct observation and accelerometry will be used to measure physical activity.

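### Children are sampled from 1st to 6th grade, but the water diary and research question 4 cover 3rd to 6th, and the water sample size makes no allowance for the difference

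*Combined protocol and SAP*

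**What the plan says.** Three places in the protocol set a grade range for the impact study.

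- Section 7.3, Participants, on sampling for the child-level measures: "boys and girls from 1st to 6th grade of primary school will be selected at random from the attendance lists of the school groups". No quota or stratification by grade is given.
- Section 7.3, Correct hydration: to study water consumption, "a Beverage Diary will be applied to participants from 3rd to 6th grade (Appendix 10". Children complete the diary at home over three days, and it yields water and sugar-sweetened beverages in ml/day.
- Research question 4, at the end of section 4: the impact question concerns physical activity, water, and "fruit and vegetable consumption in girls and boys from 3rd to 6th grade of primary school".

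The matching objective in section 6 names no grade: "To analyze the impact of the School Health Program on schoolchildren physical activity levels, water consumption, and fruit and vegetable consumption". The separate short-term results component (section 7.2) also uses the narrower range: "The questionnaire is addressed to all girls and boys from 3rd to 6th grade".

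The 24-hour recall records drinks, but the plan says that its information "will be used to evaluate the consumption of fruits and vegetables, sugar sweetened beverages (SSBs), and highly processed foods". Water is not on that list.

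The sample size text in section 7.3 assumes "a statistical power of 80%, and a correlation of 0.2 between the basal and final measurements", a design effect of 2 and 20% losses. Table 6 gives 384 for water (SD 631 ml, difference 171 ml). "A baseline measurement of 1000 girls and boys has been proposed", in 30 schools.

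**The concern.** Followed literally, the sampling sentence enrols 1st and 2nd graders who count towards the 1000 but can contribute nothing to the water outcome as the plan measures it. The water requirement takes up nearly all of the 1000, so there is little slack to absorb them. The 171 ml hypothesis would then be tested on fewer children than it was sized for, and a null result would be harder to read. The issue is precision; the estimate is not biased by it.

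The mismatch also leaves open whether fruit and vegetables and physical activity, which share research question 4, are to be analysed in grades 1 to 6 or 3 to 6.

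**Working it through.** **Inputs.** From section 7.3 and Table 6: alpha 0.05 (two-sided assumed), 80% power, correlation 0.2, SD 631, difference 171, stated water n 384, design effect 2, losses 20%, 1000 children, 30 schools. Assumed: the share of the sample in grades 3 to 6, taken as 4/6 for an even spread and varied from 60% to 75%.

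**The plan's 384.** Total n = 4 × (1.960 + 0.842)² × 631² × k / 171²:
- endline only, k = 1: 428
- ANCOVA, k = 1 − 0.2² = 0.96: about 410
- change score, k = 2(1 − 0.2) = 1.6: 684

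None gives 384. It is used below as the plan's own benchmark for 80% power, and the other bases are shown alongside.

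**Children needed for water.** 384 × 2 × 1.2 = 922, or 384 × 2 / 0.8 = 960, depending on how losses are applied. With a diary under an even spread: 1000 × 4/6 = 667.

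**Clustering.** 1000/30 = 33.3 children per school. Design effect 2 implies ICC = (2 − 1)/(33.3 − 1) = 0.031. With 667 children there are 22.2 per school, so the design effect becomes 1 + 21.2 × 0.031 = 1.66. Keeping it at 2 with 22.2 per school requires ICC = 1/21.2 = 0.047.

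**Effective n after 20% losses.**
- All 1000: 1000 × 0.8 / 2 = 400
- 667, ICC held: 667 × 0.8 / 1.66 = 322
- 667, design effect kept at 2: 667 × 0.8 / 2 = 267

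**Power** = Φ(2.802 × √(effective n / n₀) − 1.960), where n₀ is the n that gives 80%:

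| Basis (n₀) | All 1000 | 667, ICC held | 667, design effect 2 |
|---|---|---|---|
| Plan's figure (384) | 81.6% | 72.8% | 64.6% |
| ANCOVA (410) | 79.0% | 69.9% | 61.7% |
| Endline only (428) | 77.3% | 68.1% | 60.0% |
| Change score (684) | 57.2% | 48.5% | 41.7% |

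With the ICC held, the loss is about 9 points on every basis. On the 384 basis, the difference detectable with 80% power, 171 × √(384 / effective n), rises from 168 ml to 187 ml.

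**Other grade shares (384 basis).** With 75% in grades 3 to 6 and the ICC held, power is 75.6% (loss 6.0 points). With 60% it is 70.1% (loss 11.5). With the design effect kept at 2, the figures are 69.7% (loss 11.9) and 60.1% (loss 21.5).

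**If only 3rd to 6th grade is sampled**, every child is eligible for the diary and the loss is zero.

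**The case against.** The strongest reply is that the sampling sentence is a slip. Research question 4 and the diary agree on 3rd to 6th grade, and so does the separate section 7.2 component. If so, nothing is lost and only wording needs correcting. That may be right, but the documents do not settle it, and the sampling sentence is the one a field team would follow.

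A second reply is that the grade range may differ by instrument on purpose. Caregivers answer the recall and staff record intake at recess, whereas children complete the diary themselves. The plan does not give this reason, but sampling six grades and giving the diary to four is not in itself contradictory. This stands as a possible reading. It leaves the gap in the water sample size and the conflict with research question 4.

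The recall cannot fill the gap as planned, because the plan does not assign water to it.

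A reader might infer a loss of 17 points, or treat 17 as a ceiling. The documents support neither. Seventeen points needs an ICC of 0.047, whereas the plan's design effect at its own cluster size implies 0.031. Nor is 17 a maximum, since a 60% share with design effect 2 gives a larger loss.

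It is also fair to say that the choice of variance formula matters more than the grade range. The planned analysis is a difference in differences, for which the change score is the closest basis, and there power is about 57% before any grade is lost. That does not remove the grade problem, but it is why the 384 needs attention too.

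**Conclusion.** The inconsistency is in the current text and should be resolved before sampling. If the Participants sentence is followed with an even grade spread, about one third of the sample has no diary and the stated water sample size is not delivered. Power on the plan's own figure falls from about 82% to about 73%. The loss of about 9 points becomes about 6 to 12 as the share in grades 3 to 6 runs from 75% to 60%. Keeping design effect 2 in the smaller clusters is a stress case: about 17 points at an even spread, and about 12 to 21.5 over the same shares.

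These figures rest on two-sided testing, 384 taken as 80% power, 20% losses and an assumed grade share. A reader might conclude that the trial is certain to be underpowered for water because of this mismatch, or that 3rd to 6th grade must be the intended range. The documents establish neither. Under the slip reading the mismatch costs no power.

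**What to change.** Before sampling, reconcile research question 4, the Participants paragraph and the Correct hydration paragraph. Either route is defensible, and the choice belongs to the investigators.

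1. **Keep 1st to 6th grade.** Restate the water sample size and power for diary-eligible children, and state which grades are used for the other outcomes in research question 4. Fieldwork does not change; the cost is a lower stated power for water. If all of research question 4 is analysed in grades 3 to 6, fruit and vegetables (n 388) also falls, from about 81% to about 72% with the ICC held. The 595 accelerometry and SOFIT children should then be drawn from grades 3 to 6, because an even draw over six grades leaves 595 × 4/6 = 397.
2. **Sample 3rd to 6th grade**, with the same 1000 children and 30 schools. Every child is then eligible for the diary. The costs are no 1st and 2nd grade data, about 333 more diaries to hand out and code, and 6th graders rising from about 1/6 to 1/4 of the sample. If they have left by endline, that alone is 25% loss against the 20% allowed. The endline date should therefore be fixed first: the introduction starts the programme in October 2019, section 7 says October 2020, and endline is 10 months after the start.

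Under either route, correct the 384 or state the formula and inputs that produce it.

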7.3 Impact analysis (baseline measurement)

Considering that Salud Escolar aims at creating healthy school environments, the impact analysis will be focused on the evaluation of some individual and environmental indicators.

Study design

A quasi-experimental design with baseline and endline evaluation will be used in schools where the School Health Program will be implemented (intervention group), and in schools where the program will not be implemented (control group). Measurements will be made prior to the start of the school program (pre-intervention), and 10 months after its implementation (post-intervention).

Study hypothesis

Based on similar studies previously carried out in the school population (Carriedo *et al.*, 2013; Safdie, Jennings-Aburto and Lévesque, 2013; McKenzie, 2015), we hypothesized the following changes in the endline measurement among children exposed to Salud Escolar, in comparison with those in the comparison group (not exposed to the intervention program):

- water consumption will increase by 171 ml (Carriedo *et al.*, 2013),
- time engaged in MVPA will increase in total 10 minutes per day, with an increase of 4 minutes per day during school recess and 4 minutes per day during physical education classes (Haerens *et al.*, 2007),
- the percentage of girls/boys who consume fruits and vegetables daily in the school environment will increase by 6.7% (Safdie, Jennings-Aburto and Lévesque, 2013).

Sample size calculation

The impact analysis study will be carried out in 30 primary schools in Mexico City (Intervention group = 15; Control Group = 15). The number of schools included was defined to better identify the effect (with a small number of schools the effect of the intervention could be confused with the characteristics of the schools) (Soto-Estrada *et al.*, 2016). Other criteria considered were the short time available for data collection (no more than three months according to reports by the Ministry of Health based on their experience during the implementation of the Health in your School program), as well as the available funds.

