Actigraph GT3X + accelerometers (ActiGraph, LLC, Pensacola, FL, USA) will be used to assess the effect of the intervention on total physical activity (minutes per day of MVPA). Accelerometry is a method for objectively monitoring physical activity and providing rich data about users' physical activity intensities. Accelerometers will be distributed to a subsample of participants in schools by

trained staff who also will record allocation and collection of the devices (Appendix 12).

Participants will be asked to wear an accelerometer with a flexible belt, on the right side at the axillary midline, for at least 7 full days (plus one day of familiarization and the morning of the last day), including two weekend days. Wearing time will be at least for 7 days in order to maximize the number of participants with sufficient valid data (minimum wearing time of 4 days with 10 hours each day). Participants and their parents or caregivers will be explained to remove the accelerometer only during bedtime and water-based activities (e.g. swimming), clear information and a demonstration of wearing the device will be provided by trained staff (Appendix 14). To ensure the adequate use of accelerometers, a daily checklist (Appendix 13) will be used to record the use of the accelerometer every morning at the school by trained staff. This school visits will be an opportunity for the trained staff to clarify participants questions about the accelerometer. Phone messages and calls, and small incentives (stickers) at the time of verification by the staff will be used as compliance enhancing strategies.

The software ActiLife 6.13.4 will be used for accelerometer initialization prior to allocation and data download after collection. Daily MVPA will be estimated using an algorithm prepared by the research team. Freedson's cut-off points will be used to estimate the schoolchildren time per day spent at different intensities of physical activity (Department of Health & Human Services, 2018).

Other variables

Anthropometry

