and Practices” (SHPPS) study (Council of Chief State School Officers, no date), from the Health Behavior in School-Aged Children (HBSC) survey (Council of Chief State School Officers, no date), and from the School Health Environment Survey (SHES) (Kroeker *et al.*, 2006). The components of the School Audit Tool assessing the school's built physical environment were taken from the school audit tool of the Sport, Physical activity and Eating behavior: Environmental Determinants in Young people (SPEEDY) study showing acceptable validity and reliability (Jones *et al.*, 2010). The tool also includes items to characterize the school grounds, the aesthetics of the school, the supply of food and access to fast-food restaurants around the school, and the amount of class time spent on physical education (Appendix 16).

Data analysis.

For the baseline evaluation, a descriptive analysis of the sample is contemplated, estimating the means and standard deviations for continuous variables, as well as percentages for categorical variables. Descriptive variables will be estimated in the total sample and by study group. A consistency in the results from the research team and the characteristics of the schools reported in the School Audit Tool will be conducted, using paired t-tests for continuous variables and Chi-square tests for categorical variables. The statistical package Stata 14 will be used for data analysis which will be disaggregated by participants sex and age.

The impact of Salud Escolar will be estimated using a difference in difference analysis considering schools as clustering variables. Behaviors of interest will be the outcome variables and group allocation and time will be the independent variables. The effect of Salud Escolar will be tested by introducing an interaction term between time and group allocation.

Fieldwork

The fieldwork will be carried out by three teams of six members, three supervisors (one for each brigade) and a coordinator. In each team two members will apply accelerometry and anthropometry measurements, four will apply the beverage diary and the 24-hour recall. Each team is estimated to work within each school for approximately one week, which represent a total of 12 schools visited in a month and two and a half months for the full data collection at the baseline stage.

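### Total diet is measured by one 24-hour recall per child per round; if the guideline comparison is reported as a share of children meeting a recommendation, that share will be biased toward 50%

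*Combined protocol and SAP*

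**What the plan says.** All of this is in section 7.3 of the protocol.

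- **Instrument.** Under Measurements: "A 24-hour recall will be applied to mothers, fathers, or caregivers of participants responsible for feeding and preparing meals at home". The respondent is asked to "describe all the food and beverages consumed the day before the interview", and the child reports what was eaten away from the adult. The recall is described in the singular, and no repeat recall or replicate subsample appears.
- **Rounds.** Under Study design there are two: before the program and 10 months after it starts. That makes one recalled day per child per round.
- **Use.** The recall is to cover fruit and vegetables, sugar-sweetened beverages and highly processed foods. Then: "A comparison will be conducted between participants consumption against the recommendations established in the Dietary and Physical Activity Guidelines". The next sentence reads: "The proportion of schoolchildren who consume fruits and vegetables, and ultra-processed foods as outcome variables will be estimated".
- **Analysis.** Under Data analysis, means and standard deviations are planned for continuous variables and percentages for categorical ones. For impact: "The impact of Salud Escolar will be estimated using a difference in difference analysis considering schools as clustering variables". Nothing separates day-to-day variation from differences between children.

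Other instruments in the same section span several days. The beverage diary is completed at "home during three days" (grades 3 to 6), and accelerometry requires a "minimum wearing time of 4 days with 10 hours each day". The recess food record covers school food only, so it cannot supply usual total diet.

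**The concern.** Dietary recommendations describe what a child eats habitually. One recalled day is habitual intake plus that day's deviation. Averaged over children the deviation cancels, so a group mean is unbiased. It does not cancel in the spread: the one-day distribution is wider than the distribution of usual intake, and the fraction beyond a cut-off changes. More children or better interviewers do not remove this, because it is a bias and not a loss of precision.

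Section 9 says the study will supply baseline evidence and inform national scale-up. If few children truly meet a recommendation, unadjusted one-day data would overstate how many do and so understate need. If most meet it, the error runs the other way.

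**Working it through.** The plan states no share meeting a recommendation and no variance components, so there is no figure of its own to reproduce. The check asks how far a one-day share can lie from the usual-intake share.

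**Inputs**

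- Days per child per round: k = 1 (section 7.3, 24-hour recall).
- Ratio L = within-child variance / between-child variance of daily intake: not in the documents. Assumed range 1 to 3.
- True share T meeting the recommendation: not in the documents. Shown from 10% to 90%. The values 26.9% and 39.2% are the national survey figures in section 2.2 for children who frequently eat vegetables and fruits. They serve only as illustrative levels, not as the trial's cut-offs.

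**Model.** One-day intake = usual intake + day deviation, both normal. With usual mean m, between-child SD s and cut-off c:

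- True share: T = Φ((m − c)/s), so z(T) = (m − c)/s.
- Share seen with k days: S = Φ(z(T)/√(1 + L/k)).

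With k = 1 the distribution is widened by √(1 + L), which is 1.41 at L = 1 and 2.0 at L = 3.

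**Worked line.** T = 10% gives z = −1.282. At L = 1, −1.282/1.414 = −0.906, so S = 18.2%. At L = 3, −1.282/2 = −0.641, so S = 26.1%.

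| True share | Seen, L = 1 | Seen, L = 2 | Seen, L = 3 |
|---|---|---|---|
| 10% | 18.2% | 23.0% | 26.1% |
| 26.9% | 33.2% | 36.1% | 37.9% |
| 39.2% | 42.3% | 43.7% | 44.5% |
| 50% | 50% | 50% | 50% |
| 70% | 64.5% | 61.9% | 60.3% |
| 90% | 81.8% | 77.0% | 73.9% |

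The error is about 8 to 16 points at a true 10% or 90%, 6 to 11 at 26.9%, 3 to 5 at 39.2%, and zero at 50%.

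**Would averaging two days be enough?** With k = 2, a true 10% still appears as 14.8% (L = 1) to 20.9% (L = 3). Averaging removes only part of the bias.

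**Effect on a change in shares.** The illustration uses the 6.2-point difference in Table 6, purely as a size. From a true base of 26.9%, a 6.2-point rise appears as 4.7 points (L = 1) or 3.4 points (L = 3). From a base of 5% it appears as 7.3 or 6.6 points, so it is not attenuated there. With no true change, the one-day share does not change either.

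**A loose bound on L from the plan.** The sample size section assumes a correlation of 0.2 between baseline and final measurements. If that held for recall intake and all of the imperfect correlation were day-to-day variation, L would be (1 − 0.2)/0.2 = 4. Part of it must be real change, so on that assumption 4 is a ceiling. At L = 4 a true 10% appears as 28.3%.

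**The case against.** The best reply is that the protocol never says outright that a share meeting each recommendation will be reported. The proportion it names can be read as children who ate the food on the recalled day, which one recall estimates validly if so labelled. Data analysis already plans means, so comparing group means with the recommendations fits the text. This stands, and it is why the point is conditional. The wording still refers to participants' consumption, the next sentence makes proportions the outcomes, and nothing rules out the adequacy share.

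Three stronger readings are tempting, and the documents do not support them.

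- **That several times too many children would be shown as meeting the fruit and vegetable recommendation.** Take the 400 g/day in section 3.1 as cut-off, with an assumed mean of 250 g and between-child SD of 80 g. A true 3.0% then appears as 9.2%, 14.9% or 20.1% for within-child SDs of 80, 120 or 160 g. But the 400 g is a background WHO figure, not the cut-off in the Mexican guidelines that the comparison uses, and every intake value is invented. The case also sits in a low tail, where relative inflation is greatest. At a within-child SD of 160 g the normal model has about 8% of one-day intakes below zero.
- **That day-to-day noise would produce a spurious program effect.** The same method is used in both groups and both rounds, so the distortion applies alike and can only rescale a real effect on shares.
- **That the main hypotheses are compromised.** The fruit and vegetable hypothesis concerns consumption at school, which is assigned to food weighing. Water rests on the three-day diary, which also records sugar-sweetened beverages in grades 3 to 6. Physical activity does not use the recall.

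**Conclusion.** The point holds as a conditional one of minor severity. The plan has one recalled day per child per round, a comparison with recommendations, proportions as outcomes and no usual-intake adjustment. If the comparison is reported as the share of children meeting a recommendation, that share is pulled toward 50%. The distortion reaches 8 to 16 points at a true 10% or 90% and vanishes at half.

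The direction follows from the design. The sizes rest on a normal model and an assumed variance ratio of 1 to 3. With skewed intakes the figures would differ and the neutral point need not fall exactly at half. Group means, and differences in means between groups and rounds, are not biased by using one day. What is exposed is guideline adequacy from the recall, chiefly for fruit and vegetables and highly processed foods.

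**What to change.** In section 7.3, under the 24-hour recall and Data analysis:

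1. Analyse recall intake as group means (g/day or ml/day) in the difference-in-difference model, and compare group means with the recommendations.
2. Label any proportion from the recall as 'consumed on the recalled day'.
3. State that the share meeting a recommendation will not be reported from unadjusted single-day data.
4. If an adequacy share is still wanted, estimate it with a usual-intake model and show it over a stated range of within-child variance.

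For step 4, control children's baseline and endline recalls, after removing the time effect, can supply a within-child variance. It is an upper-bound sensitivity value only: recalls 10 months apart include real change, so using it as the estimate would tend to over-correct. It also becomes available only after endline, so it cannot serve a baseline report. A repeat recall in a subsample would give a cleaner value, at the price of extra fieldwork.

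Cost: steps 1 to 3 are wording changes, and step 4 adds a little analysis. The loss is that no unadjusted adequacy share can be given at baseline, and a group mean does not show how many children fall short.
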